13.7 Record Retention	60
References	61
Appendix I: Performance Status/Scores	64
Appendix II: Biology Studies Collection and Shipping forms	65
Appendix III: Pharmacopeia Library	67
Appendix IV- Example expression file format for the VCF 4.1:	69

PROTOCOL SYNOPSIS

PROTOCOL TITLE	Molecular-guided therapy for the treatment of patients with relapsed and refractory childhood cancers
PROTOCOL NUMBER	NMTRC009
PHASE OF DEVELOPMENT	Feasibility
OBJECTIVES	
Primary Determine feasibility of using tumor samples to assess genomic sequencing using predictive modeling to make real-time treatment decisions for children with relapsed/refractory cancers
 
Secondary
 
 • To determine the activity of treatments chosen based on: 
 • Overall response rate (ORR) • Progression free survival (PFS) • To continue to evaluate the safety of allowing a molecular tumor board to determine individualized treatment plans • (Voluntary) To explore the relationship between tumor phenotype/genotype and response by permitting use of tumor tissue in a correlative biologic study • To compare PFS interval to PFS intervals of previous chemotherapy regimens since relapse for each subject. • Sub analysis examination of disease types.
STUDY DESIGN	
A prospective open label, multicenter study to evaluate the feasibility of molecularly guided therapy in patients with relapsed or refractory childhood cancers
 
A total of 200 evaluable subjects with childhood cancer that are refractory to or have relapsed on conventional therapy will be treated with molecular guided therapy. Additional patients may enroll through compassionate access if no other treatment options are available.
 
Subjects will be evaluated in 3 strata:
 
 • Stratum 1: 50 subjects with refractory/relapsed neuroblastoma • Stratum 2: 50 subjects with relapsed or refractory brain tumors • Stratum 3: 100 subjects with refractory or relapsed rare tumors 
Guided therapy will allow the use of individualized therapeutic combinations (up to 4 agents). All subjects will be followed for survival, disease response, progression and safety. All subjects will be treated according to the discretion of the treating oncologist and study committee (minimum 3 oncologists and one pharmacist). Extent of disease will be measured and assessed for changes throughout the course of the study.

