ESTIMATED NUMBER OF PATIENTS/GEOGRAPHIC REGIONS	
200 evaluable (220 total) relapsed/refractory pediatric cancer patients. Additional patients may enroll through compassionate access if no other treatment options are available.
 
Patients will enroll at:
 
Arnold Palmer Children's Hospital, FL St. Louis University/Cardinal Glennon Children's Medical Center, MO Helen DeVos Children's Hospital, MI Levine Children's Hospital, NC Connecticut Children's Medical Center, CT Children's Mercy Hospital, Kansas City MO Rady Children's Hospital of San Diego, CA Medical University of South Carolina, SC Monroe Carrell Jr. Children's Hospital at Vanderbilt, TN Kapiolani Medical Center for Women and Children, HI Dell Children's Hospital, TX Texas Children's Hospital, Baylor College of Medicine, TX Primary Children's Hospital, UT Children's Hospital and Clinics of Minnesota, MN Penn State Milton S. Hershey Medical Center and Children's Hospital, Hershey, PA Arkansas Children's Hospital – Little Rock, AR 
International Sites
 American University of Beirut Medical Center, Lebanon La Timone; Marseille, France

LENGTH OF STUDY	Accrual to this study is estimated to be approximately 3-4 years.
STUDY ASSESSMENTS	Refer to Table of Assessments for timing of study procedures.
CRITERIA FOR EVALUATION	
Feasibility Measures: Primary objective: The definition of feasibility for this study will include: “Enrollment onto study, genomic profile, analysis and report generation completed, tumor board held with treatment decision, treatment review completed, start of treatment, and completion of 1 cycle of therapy.”
 
Efficacy Measures: Secondary objectives Response: To determine the overall response rate (ORR) by the presence of radiologically assessable disease by cross-sectional CT or MRI imaging and/or by MIBG or PET scans.
 
 ◆ Duration of response, defined as the period of time from when measurement criteria are met for complete response (CR) or partial response (PR), whichever is first recorded, until the first date that recurrent or progressive disease (PD) is objectively documented (taking as reference for PD the smallest measurements recorded since the treatment started) ◆ The assessment of response will include the initial measurable

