	
targets and will be performed after cycle 2, then after every other cycle.
 
 • A subject will be defined as a responder if CR/PR is observed at any time of the treatment • Clinical response will be seen if stable disease and decrease in tumor markers by $\geq 50\%$ or CR of bone marrow. • Time to progression, defined as the period from the start of the treatment until the criteria for progression are met taking as reference the screening measurements • Comparisons of ORR and PFS for the first and second cohorts of 100 patients (i.e., those who enroll prior to versus after the implementation of Amendment 3.0, respectively) will be performed. 
Safety Measures: Secondary objectives
 
 • Safety analysis will be conducted on all subjects who have received at least one dose of therapy, and will include the frequency of all reported adverse events and laboratory abnormalities as well as frequency of dose interruptions, dose reductions and treatment discontinuation.
STATISTICS/SAMPLE SIZE ESTIMATE	
200 evaluable subjects
 
Patients who enroll following implementation of Amendment 3.0 (second cohort of 100 patients) will have their tumor biopsies analyzed using an updated Drug Prediction Report (Appendix III). Overall Response Rate (ORR) and Progression Free Survival (PFS) for this group will be compared to those of the first 100 patients who received treatment based upon the original Drug Prediciton Report and Pharmacopeia Library.

TABLE OF PROCEDURES AND ASSESSMENTS

Procedure	Screening	Cycle 1 Day 1	Cycle 1 Day 8	Cycle 1 Day 15	Cycle 1 Day 22 (if applicable)	Subsequent Cycles Day 1	Off Therapy/ 30 Day Follow-up
Informed consent	X						
Demographics	X						
Medical history	X	X	X	X	X	X	
Baseline Symptom Form	X	X					
Concurrent meds	X	X				X	X
Physical exam	X	X	X	X	X	X	X
Vital signs	X	X	X	X	X	X	X
Height	X	X				X	
Weight	X	X				X	X
Karnofsky or Lansky play score	X	X		X		X	X
CBC w/diff,	X	X	X	X	X	X	X
Serum chemistry *	X	X		X		X	X
Tumor Markers **	X	X				X	X
Adverse events			X	X	X	X	X
Surgical resection &/or diagnostic biopsy	X						
MRI or CT***	X						
MIBG/PET ***	X						
Bone Marrow (any subject suspected to have BM disease) ^	X						
B-HCG	X						
EKG (as indicated)		X					

* Serum electrolytes, BUN, Creatinine, Bilirubin, ALT, AST

**LDH and/or Specific Tumor Markers for defined disease (if available)

***Type of scan as indicated for disease type

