The primary objective of this feasibility study was to evaluate the feasibility and safety of using predictive modeling based on genome-wide mRNA expression profiles of neuroblastoma tumor biopsies to make real-time treatment decisions. Feasibility was defined as “enrollment onto study, quality mRNA obtained, gene chip completed, tumor board held, medical monitor review and approval, start of treatment by 21 days post biopsy/surgical resection date, and completion of 1 cycle of therapy.” Sixteen (16) subjects were enrolled to this study, all with multiply relapsed or refractory neuroblastoma. Subjects were between 1-11 years post diagnosis. All subjects had soft tissue disease which was able to be biopsied. All biopsies were adequate by pathology evaluation (>75% viable tumor) and RNA quality (>6.5 RIN). 2 subjects were deemed ineligible due to tumor type after biopsy. Gene chips were completed in 3-8 days (95% CI: 3.8 – 6.8), report generation took 0-3 days (95% CI: 0.0 – 1.5), tumor board took 1-6 days (95% CI: 1.6 – 4.2), medical monitor sign off took 1-2 days (95% CI: 0.8 – 1.4). The total time from date of biopsy to tumor board was 6-11 days (95% CI: 7.5 – 10.2) for all subjects and 7-20 days to treatment (95% CI: 8.9 – 16.1), with an average of 12.4 days. The tumor board which consisted of 4-15 pediatric oncologists from sites across the US and a pediatric oncology pharmacist was able to create individualized therapy regimens for all subjects. Correlative biology specimens were obtained and grown in culture. Mice xenograft establishment is ongoing. Cultures and xenografts are able to be used for validation studies of predicted drug sensitivity. Triplicate biopsies showed reproducible sets of drugs and the comparatively large differences in drug lists between patients show that the drug lists are tailored to patients. Comparison of RNA expression profiles with RNA sequencing from each patient showed strong correlation.

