The study endpoint showed that 14/14 patients were feasible to enroll, biopsy, genomic analysis, tumor board review and patient treatment was met. All regimens were found to be safe by the medical monitor proving that the molecular tumor board was able to make safe decisions similar to hospital tumor boards making treatment decisions without molecular information on the patients. It was felt that the pharmacy review for evaluating drug-drug interactions and deciding on laboratory and safety testing was an important part of the tumor board (this is not usually present at hospital tumor boards) and will continue to be incorporated in this and future trials. All patients tolerated therapy well and were treated without any serious adverse events related to study drugs. Clinical benefit was seen 64% of patients. This study shows that it is feasible to create therapeutic treatment plans based on genomic profiling in real time and that patients are able to be treated safely on a tumor board derived molecular guided therapy using existing medications

In this study we proposed to study reproducibility by applying it to triplicate samples obtained by dissecting each of five solid tumors. The primary goal of the reproducibility study is to evaluate the variation among sets of drug therapies associated with the same tumor. Secondary goals are 1) to compare the variation among sets of drug therapies from the same tumor with variation

between tumors from distinct patients and 2) to evaluate variation associated with earlier steps in the process, in particular, expression profiles and comparative expression profiles.

Distance-based nonparametric multivariate analysis of variance [41, 42] allowed us to reject the null hypothesis that variation between biopsies can be accounted for by the variation within biopsies ($p=0.001$). That the variation among expression profiles associated with the same biopsy is small compared with the variation between expression profiles associated with different biopsies is apparent from Principal Component Analysis (Figure 1).

Sets of drug therapies

Similarly, the variation among drug sets associated with the same biopsy is small compared with the variation among drug lists associated with different biopsies ($p=0.001$). The reproducibility averaged over patients, replicates, and drugs is 0.68. As the threshold score increases the reproducibility increases to 1 (Figure 2).

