12.3 Process and Feasibility Analysis

Each of the process measures including the total time to treatment initiation and time to completion of the first cycle of treatment will be described using standard descriptive methods such as means, medians, standard deviations, and 95% confidence intervals. The total time duration to treatment initiation and time to completion of the first cycle of treatment will also be examined using Kaplan-Meier plots since some patients who are considered process failures or who do not complete the full duration to the completion of the first cycle of treatment may contribute censored data. The formal hypothesis testing of the feasibility or success is based upon the 2-stage Mini-Max testing process outlined in Section 8: *Sample Size Justification*. Further quantification of the feasibility success rate will be based upon the percentage of the $n = 16$ patients in each strata who achieve the specified overall time frame limits. This success rate will be supplemented with an exact 95% confidence interval using a Binomial distribution model due to the small sample size involved.

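### Section 12.3 still takes its only feasibility percentage from 16 patients per stratum, plans no success rate for the second 100 subjects on the updated Drug Prediction Report, and scores success on time limits that the endpoint does not contain

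*Combined protocol and SAP*

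**What the plan says.** **Analysis.** Section 12.3 refers the formal test to the two-stage rule in Section 8. It then quantifies success further as the "percentage of the $n = 16$ patients in each strata who achieve the specified overall time frame limits", and adds an "exact 95% confidence interval using a Binomial distribution model due to the small sample size involved". The same section plans summary statistics for the process measures, and Kaplan-Meier plots of time to treatment start and time to completion of cycle 1. No sample size is attached to those.

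**Endpoint.** The Synopsis (Criteria for Evaluation) and Section 8 define feasibility as a chain of steps running from enrolment and genomic reporting through "tumor board held with treatment decision, treatment review completed, start of treatment, and completion of 1 cycle of therapy". No step has a deadline, and neither does the chain as a whole.

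**Size.** The Synopsis plans "200 evaluable (220 total) relapsed/refractory pediatric cancer patients". Strata 1 and 2 have 50 subjects each, and stratum 3 has "100 subjects with refractory or relapsed rare tumors".

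**Purpose of the enlargement.** Section 8 reports that 100 subjects had enrolled by Amendment 3.0 and that feasibility had been met in every stratum. It gives further feasibility evidence with the new Drug Prediction Report as one reason for the extra subjects, together with safety and efficacy data. For the two cohorts, the Synopsis plans "Comparisons of ORR and PFS for the first and second cohorts of 100 patients", and Section 8 repeats this. Neither plans a feasibility rate by cohort.

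**The concern.** Feasibility is the primary objective. The sample size and the prediction report both changed at Amendment 3.0, but the feasibility percentage in Section 12.3 was not extended to match. This has two consequences.

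- The question that partly justifies the second 100 subjects has no planned success rate or interval. The completed test cannot supply one, because Section 8 says that the first 100 were treated on the earlier report.
- The percentage is scored on time limits, while the endpoint is scored on completion of steps. One analyst could count completed steps. Another could borrow a deadline from elsewhere in the protocol. Both could claim to follow the plan, and their rates could differ.

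**Working it through.** **1. The plan's own design figures.** The inputs from Section 8 are a null rate of 0.50, an alternative of 0.75, a stop at 5 or fewer successes in 9, and rejection of the null at 11 or more in 16.

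Probability of stopping early = Σ C(9,x) pˣ(1−p)⁹⁻ˣ for x = 0 to 5.

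- At p = 0.50: (1+9+36+84+126+126)/512 = 382/512 = 0.746.
- At p = 0.75: 0.166.

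Both match Section 8.

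Probability of rejecting the null = Σ P(X₁ = x)·P(X₂ ≥ 11−x) for x = 6 to 9, with X₂ binomial on 7 patients.

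- At p = 0.50: 0.088, within the 10% limit.
- At p = 0.75: 0.753, above the 75% target.

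A search over smaller totals finds no two-stage design below 16 that meets both limits. The design is correct as stated.

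**2. Coverage of the percentage.** 3 × 16 = 48, and 48/200 = 24%. By stratum, 16/50 = 32% in strata 1 and 2, and 16/100 = 16% in stratum 3. Section 12.3 does not say which 16. Because Section 8 reports feasibility met in all strata by Amendment 3.0, they presumably come from the first 100. In that case no subject on the updated report enters the percentage.

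**3. Precision.** Exact (Clopper-Pearson) 95% limits: the lower is the 0.025 quantile of Beta(x, n−x+1) and the upper is the 0.975 quantile of Beta(x+1, n−x). When x = n, the lower limit is 0.025^(1/n) and the upper is 1. The counts are illustrative. The first group sits near the Section 8 alternative of 75%. The second is complete success, as the earlier neuroblastoma trial reported ("14/14 patients were feasible to enroll").

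| Denominator | Near 75% | 95% interval | Width (points) | All succeed: 95% interval |
|---|---|---|---|---|
| 16 (Section 12.3) | 12/16 | 47.6–92.7% | 45 | 79.4–100% |
| 50 (stratum 1 or 2) | 38/50 | 61.8–86.9% | 25 | 92.9–100% |
| 100 (second cohort, or stratum 3) | 75/100 | 65.3–83.1% | 18 | 96.4–100% |
| 25 (stratum 1 or 2 within one cohort, if evenly split) | 19/25 | 54.9–90.6% | 36 | not computed |

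The last row assumes an even split of each stratum across cohorts, which the documents do not state. Crossing stratum with cohort therefore gains little: 36 points against 45.

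**4. Criterion, side by side.**

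- Section 12.3 counts patients who meet overall time limits and calls those limits specified.
- The Synopsis and Section 8 state the endpoint without any.
- Section 1.2 gives the earlier neuroblastoma trial a deadline, "start of treatment by 21 days post biopsy/surgical resection date, and completion of 1 cycle of therapy", and its successor trial also had 21 days. This trial's definition omits it.
- Section 8 mentions windows of 7–10 days and 5 days when reporting 5 preliminary subjects.
- Section 9.6 gives single-step timings: tumor board within 4 days of the report, and treatment within 1 week of the discussion with parents.

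None of these is an overall limit stated for this trial. The two criteria can also separate in practice. Section 3.6 allows a cycle of other therapy before board-defined treatment, so a subject could complete every step and still miss a short deadline.

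**5. Denominator.** The Synopsis plans 220 subjects for 200 evaluable. As a hypothetical extreme, suppose that all 200 evaluable subjects succeed and the other 20 are process failures. The all-enrolled rate is then 200/220 = 90.9% (86.3–94.4%) instead of 100%. Nothing in the documents says that those 20 would be failures. The example shows only that the denominator has to be named.

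**The case against.** The strongest reply is that 16 is the right denominator for the test it accompanies. Section 12.3 places the percentage directly after the two-stage rule, and Section 8 says that the rule was met. This stands. A reader might infer that the design is too small, that the feasibility finding is unsafe, or that the n = 16 rate should be deleted. The documents support none of these. The design figures reproduce, and the rate belongs to the completed test.

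A second reply is that the process summaries and Kaplan-Meier plots are not limited to 16, and that a curve of time to completing cycle 1 implies a completion proportion. This stands in part, so it would be wrong to say that the plan describes nothing about later subjects. But Section 12.3 treats process failures as possible censored observations, which would bias such a proportion. It also does not split the plots by cohort or report version.

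A third reply is that a limit may exist after all. Section 9.6 refers to a flow chart that is missing from the extracted text. Section 8 also says that the preliminary results fit the expected performance standards, so its windows may be intended. This stands too. A reader might conclude that the trial has no time limit anywhere, and the readable text cannot establish that. It does show that the endpoint definition contains none, while Section 12.3 scores on one.

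Finally, first-cohort feasibility is already known, so a new rate for that cohort cannot be presented as prespecified. This is right, and the fix reflects it.

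**Conclusion.** The point holds as a gap and a mismatch in Section 12.3, and it should be fixed. Followed as written, the only feasibility percentage rests on 24% of the planned evaluable subjects. It gives no success rate for the updated report, and it uses a criterion that the primary endpoint does not share. At about the 75% target, the second cohort of 100 would give an interval 18 points wide, against 45 at n = 16. The smaller gain within stratum-by-cohort cells is a reason to report the cohort overall.

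The conclusion rests on the readable text, on the presumption that the 16 per stratum come from the first 100, and on illustrative success counts. The coverage and missing-rate parts do not depend on the flow chart. The wording mismatch with the endpoint would also remain if the chart contained a limit. The completed test is unaffected. The percentage is descriptive, so the harm is incomplete and ambiguous reporting of the primary objective, not an invalid result.

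**What to change.** Leave the two-stage test and its n = 16 rate in place, labelled as the report of that test. Add to Section 12.3:

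- **Rate.** The proportion of all enrolled subjects who complete the Section 8 steps, with exact 95% interval.
- **Groups.** The post-Amendment 3.0 cohort overall, as a prespecified rate. Also the pre-Amendment cohort and each full stratum, labelled as defined after the first-cohort feasibility result was known.
- **Denominator.** Show the rate among evaluable subjects alongside, with that term defined for feasibility. State how enrolled subjects without an adequate specimen (Section 2.3) and compassionate-access subjects (named in Section 12.4 only for secondary analysis) are counted.
- **Criterion.** Score success on the endpoint as Section 8 defines it. If the sponsor intends a time limit, state it and report the within-limit proportion as a separate, additional rate, saying how subjects who take the interim cycle are counted.

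The cost is a wording change made by protocol amendment with IRB review (Section 13.2). No new visits or data are needed, because the steps already form the primary endpoint. The downside is slightly more analysis, and an all-enrolled rate that may be lower than the evaluable rate: by 100 − 90.9 = 9.1 points in the hypothetical extreme above.

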12.4 Secondary Data Analysis

Overall response rates (ORR) will be examined using rates for each of the clinical response categories supplemented using exact 95% confidence intervals. Progression free survival (PFS) data for each of the three clinical strata will be examined using Kaplan-Meier time to event plots. Differences in the PFS for the current treatment protocol with historical PFS values will be explored using Cox proportional hazard rate methods when possible. Patients that enroll through compassionate access will be included in secondary data analysis.

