- x. Ethesioneuroblastoma (At relapse after standard of care therapy and/or non- responsive/progressive to accepted curative chemotherapy).
- xi. Neuroendocrine tumors (At relapse after standard of care therapy and/or non- responsive/progressive to accepted curative chemotherapy).
- xii. Desmoplastic small round cell tumor (At relapse after standard of care therapy and/or non- responsive/progressive to accepted curative chemotherapy).
- xiii. Melanoma (At relapse after standard of care therapy and/or non- responsive/progressive to accepted curative chemotherapy).

2. Subjects must be age \geq 12 months at enrollment
3. Subjects must be age \leq 21 years at initial diagnosis
4. Subjects must have measurable disease as defined by RESIST v1.1 at the time of biopsy and tumor must be accessible for biopsy. Tumor samples submitted for analysis must contain $>50\%$ viable tumor tissue to qualify. In addition, subjects with disease confined to the bone marrow are eligible to enroll if the degree of marrow involvement is expected to be $>50\%$.
Note: Subjects who are expected to have no evidence of disease after surgical removal of their tumor are still eligible for this trial if their disease would normally require adjuvant chemotherapy treatment after surgery despite NED status.
5. Current disease state must be one for which there is currently no known effective therapy
6. Specimens will be obtained only in a non-significant risk manner and not solely for the purpose of investigational testing.
7. Lansky or Karnofsky Score must be ≥ 50
8. Subjects without bone marrow metastases must have an ANC $> 750/\mu\text{l}$ to begin treatment.
9. Subjects with CNS disease currently taking steroids must have been on a stable dose of steroids for 2 weeks prior to their biopsy and must not have progressive hydrocephalus at enrollment.
10. Adequate liver function must be demonstrated, defined as:
 - a. Total bilirubin $\leq 1.5 \times$ upper limit of normal (ULN) for age AND
 - b. ALT (SGPT) $< 10 \times$ upper limit of normal (ULN) for age
11. A negative serum pregnancy test is required for female participants of child bearing potential (≥ 13 years of age or after onset of menses)

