Assumptions: The feasibility outcome is a binary measure for each of the three clinical strata with a lower success null value of 50% which would require reconsideration of the full process and an upper success value of 75% for the alternative which would be deemed worthy of further consideration for an efficacy trial at the next phase. A binomial distribution was used for the testing process with a combination of Type I error levels (10%) and Power (75%). The basic design overall is a MiniMax approach which minimizes the overall sample size. **The MiniMax design with an interim look will require an overall sample size of n = 16. Each of the three clinical strata will use a two-stage decision rule.**

The Two-Stage Stopping Rule for each of the three strata is as follows:

Stage 1: Stop and accept the null hypothesis if the observed feasibility rate is less than or equal to 5/9. Otherwise, continue to stage 2.

The probability of stopping for futility is 0.746 when H_0 is true and 0.166 when H_a is true.

Stage 2: Stop and accept the null hypothesis if the observed feasibility rate is less than or equal to 10/16. Otherwise, stop and reject the null hypothesis.

As of Amendment 3.0, 100 subjects have been enrolled and all feasibility measures for all strata have been met. To gain additional feasibility with the new Drug Prediction Report and additional safety and efficacy data, additional subjects will be enrolled to meet a revised goal of 200 total evaluable subjects.

The expanded access for 100 patients will enroll following implementation of Amendment 3.0. Their tumor samples will be analyzed using an updated Drug Prediction Report (Appendix III). Overall Response Rate (ORR) and Progression Free Survival (PFS) for this group will be compared to those of the first 100 patients who received treatment based upon the original Drug Predictiton Report and Pharmacopeia Library.

9 Laboratory Evaluations

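### Compassionate-access patients, additional to the 200 and without a stated cap, are pooled into ORR and PFS with no separate display, and their place in the Amendment 3.0 cohort comparison is unclear

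*Combined protocol and SAP*

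**What the plan says.** The Synopsis sets the size at "200 evaluable (220 total) relapsed/refractory pediatric cancer patients", in strata of 50, 50 and 100, and then adds: "Additional patients may enroll through compassionate access if no other treatment options are available". It gives no number or ceiling for this route, and the protocol has no eligibility section specific to it.

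Section 12.4 plans exact 95% confidence intervals for ORR, Kaplan-Meier plots of PFS by stratum, and exploratory Cox comparisons with historical PFS where possible. It ends with the rule "Patients that enroll through compassionate access will be included in secondary data analysis". No separate summary, stratification or sensitivity analysis by route of entry is mentioned.

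The Synopsis (Criteria for Evaluation) lists among the secondary efficacy measures "Comparisons of ORR and PFS for the first and second cohorts of 100 patients", explained as "those who enroll prior to versus after the implementation of Amendment 3.0, respectively". Section 8 repeats the comparison and introduces the second group with a further term: "The expanded access for 100 patients will enroll following implementation of Amendment 3.0". Section 12.4 does not mention this comparison.

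**The concern.** Two things are at stake.

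The first is the secondary estimates. A response rate with an exact interval is interpretable only if the reader knows whom the denominator represents. Here it is the protocol subjects plus an open number of others, and the plan does not say whether those others met the eligibility criteria, had measurable disease, or were assigned to a stratum.

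The second is the cohort comparison. It is the planned look at whether activity changed when the updated Drug Prediction Report came in, and it is not randomised. If compassionate-access patients count in it and most enter on one side of Amendment 3.0, a difference between routes of entry would appear as a difference between report versions. The reported tables would give no means of telling the two apart.

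**Working it through.** **The plan's own calculation.** The only design figure is the two-stage feasibility rule in Section 8 (stop at 5/9 or fewer, fail at 10/16 or fewer, 50% against 75%). Exact binomial calculation gives:

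- probability of early stopping 0.7461 at 50% and 0.1657 at 75%, matching the stated 0.746 and 0.166;
- type I error 0.0878 and power 0.7532, within the stated 10% and 75%.

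No two-stage design with fewer than 16 subjects meets those limits. The design reproduces, and the Section 12.4 sentence concerns only secondary analyses, so the primary test is untouched. The documents give no design figure for ORR, PFS or the cohort comparison.

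**Who is in the cohort comparison.** The Synopsis wording can be read in two ways:

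- Cohorts of 100 patients each: the size is fixed, so additional patients stay out.
- Enrolment before or after Amendment 3.0: membership goes by date, so additional patients come in.

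The blanket inclusion in Section 12.4 leans towards the second reading, since ORR and PFS are secondary measures. But that section never names the comparison, so the question stays open.

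**Effect on one cohort's ORR.** The documents give neither a response rate nor a number of compassionate-access patients, so every rate and count below is an assumption. With a protocol ORR of 15% in 100 subjects and k extra patients with response rate p:

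pooled ORR = (100 × 0.15 + k × p) / (100 + k)

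- k = 20, p = 5%: (15 + 1)/120 = 13.3%
- k = 20, p = 0%: 15/120 = 12.5%
- k = 40, p = 5%: (15 + 2)/140 = 12.1%
- k = 40, p = 0%: 15/140 = 10.7%
- any k, p = 15%: 15%, no shift

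The shift equals k/(100 + k) × (p − 0.15). The first factor is always below 1, so the shift cannot exceed the difference between the two groups' rates, however many patients enter.

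**Effect on the comparison, in both directions.** Assume a protocol ORR of 20% in both cohorts, no true cohort effect, and all m extra patients in the second cohort. The plan names no test; a two-sided 5% pooled two-proportion test (normal approximation) is used here for scale. Worked case, m = 50 at 0%:

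- second-cohort rate 20/150 = 13.3%, difference d = −6.7 points;
- pooled rate 40/250 = 0.16, null SE = √(0.16 × 0.84 × (1/100 + 1/150)) = 0.0473;
- actual SE = √(0.16/100 + 16/150²) = 0.0481;
- lower-tail probability Φ((−1.96 × 0.0473 + 0.0667)/0.0481) ≈ 0.29; the upper tail is negligible.

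| Extra patients m | Their ORR | Pooled ORR, 200 + m | Spurious cohort difference (points) | Chance of nominal 5% rejection |
|---|---|---|---|---|
| 20 | 0% | 18.2% | −3.3 | 10% |
| 20 | 10% | 19.1% | −1.7 | 6% |
| 20 | 30% | 20.9% | +1.7 | 6% |
| 50 | 0% | 16.0% | −6.7 | 29% |
| 50 | 10% | 18.0% | −3.3 | 11% |
| 50 | 30% | 22.0% | +3.3 | 9% |
| 100 | 0% | 13.3% | −10.0 | 66% |
| 100 | 10% | 16.7% | −5.0 | 20% |
| 100 | 30% | 23.3% | +5.0 | 15% |

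With few extra patients, or similar outcomes, the effect is small. It is material only with many patients and a large difference in response.

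**The case against.** The strongest reply is that nothing documents a different population. The one stated condition for compassionate access closely resembles inclusion criterion 5, "Current disease state must be one for which there is currently no known effective therapy", and criterion 1 also requires disease without known effective curative therapy or refractory disease. No section waives eligibility or describes a different treatment process. This stands: a reader might infer that these patients are differently selected, but the documents do not establish it. What remains is that a patient who met every criterion while a place was open could enrol through the ordinary list in Section 5.1. A separate route therefore suggests either unmet criteria or no open place. That too is inference, because the protocol does not explain the route.

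A reader might also take it as settled that these patients enter the cohort comparison. It is not: the cohort size is stated as 100, Section 8 gives 100 for each group, and the enrolment-date phrase can be read as a gloss on those fixed cohorts. This is an ambiguity to resolve.

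The stakes are limited as well. ORR and PFS are secondary, no decision rule attaches to them, and the inclusion is openly prespecified. The assumed fall from 15% to between 10.7% and 13.3% lies well inside the exact 95% interval for 15/100, about 8.6% to 23.5%. These points lower the urgency. They do not explain why the two routes should never be shown apart.

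Finally, restricting the headline analysis to the 200 evaluable subjects would be a poor remedy. The documents do not define evaluable, and if it required a completed cycle, early progressors could be dropped. This stands, and the fix below avoids that set.

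**Conclusion.** The concern holds in a limited form. Section 12.4 pools an additional, uncapped group into ORR and PFS without any separate or sensitivity display. The documents leave open whether that group must meet eligibility and whether it counts in the Amendment 3.0 comparison. Confounding by route of entry would follow only if outcomes differ and the patients cluster in one cohort.

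The size cannot be determined from the documents. Under the assumed 15% protocol ORR the shift in one cohort of 100 is 1.7 to 4.3 points downward for 20 to 40 patients at 0 to 5%, zero at equal rates, and upward if their response is better. A reader might infer from the missing cap that the shift has no limit; that is wrong, because a pooled rate always lies between its two component rates.

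The change is worth making before analysis because it is nearly free. It does not threaten the primary feasibility conclusion.

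**What to change.** Replace the last sentence of Section 12.4 with wording to this effect:

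> ORR and PFS will be reported for protocol-enrolled subjects who received study treatment, for compassionate-access patients separately, and for both groups pooled. The comparison of subjects enrolled before and after Amendment 3.0 will use protocol-enrolled subjects only; a sensitivity analysis will add compassionate-access patients.

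State the same rule for the comparison in the Synopsis (Criteria for Evaluation and Statistics) and in Section 8. In Section 8, say whether expanded access means the second protocol cohort or the compassionate-access route. State also whether compassionate-access patients must meet Sections 4.1 and 4.2, and make sure the route of entry is recorded for each patient. The safety analysis needs no change, since it already covers every subject who received at least one dose.

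The cost is short edits in three places, a slightly smaller n for the headline estimates, and a few extra tables. No data are lost.
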